3.10.3 Analysis of Safety Endpoints

AEs will be coded using the Medical Dictionary for Regulatory Activities (MedDRA) and the following information will be summarized:

- Overall AEs will also be described according to seriousness, severity, action taken with study drug, relationship to study drug and outcome of AE.
- The total number of AEs, the total number and proportion of patients experiencing at least one AE during the treatment period will be summarized by system organ class (SOC) and preferred term (PT). To count the number of patients who experience each AE, patients experiencing the same AE multiple times will only be counted once for the corresponding PT. AEs will be tabulated presenting the SOCs alphabetically.
- AEs will also be summarized as described above for serious adverse events (SAEs).

Furthermore, the analysis of these safety endpoints will compare the incidence in the short tirofiban treatment group to the incidence in the eptifibatide group, the incidence in the short tirofiban treatment group to the incidence in the long tirofiban treatment group and the incidence in the long tirofiban treatment group to the incidence in the eptifibatide group, by using the Fisher’s mid-p test (Berry and Armitage, 1995) and Student t-test for binary and quantitative safety outcomes,

respectively. Serious adverse events will also be tabulated overall and by severity for each treatment group.

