- *Secondary outcome 2: PPM within 48 hours following PCI or hospital discharge, whichever comes first*
- *Secondary outcome 3: uTVR within 48 hours following PCI or hospital discharge, whichever comes first*
- *Secondary outcome 4: death within 48 hours following PCI or hospital discharge, whichever comes first*
- *Secondary outcome 5: death, PPM, uTVR or major bleeding within 48 hours following PCI or hospital discharge, whichever comes first, where PPM is defined as at least one troponin elevation of ≥ 10 times the upper limit of normal and at least 20% of greater than the baseline troponin value, per the troponin Local Laboratory within 48 hours following PCI or hospital discharge, whichever comes first (a non-inferiority margin of 12.4% will be used for the short tirofiban versus eptifibatide comparison)*
- *Secondary outcome 6: at least one troponin elevation of ≥ 10 times the upper limit of normal and at least 20% of greater than the baseline troponin value, per the troponin Local Laboratory, within 48 hours following PCI or hospital discharge, whichever comes first (a noninferiority margin of 12.4% will be used for the short tirofiban versus eptifibatide comparison)*
- *Secondary outcome 7: at least one troponin elevation of ≥ 20 times the upper limit of normal and at least 20% of greater than the baseline troponin value, per the troponin Local Laboratory, within 48 hours following PCI or hospital discharge, whichever comes first*
- *Secondary outcome 8: at least one troponin elevation of ≥ 50 times the upper limit of normal and at least 20% of greater than the baseline troponin value, per the troponin Local Laboratory, within 48 hours following PCI or hospital discharge, whichever comes first*

Note: This table will also be repeated for Per-Protocol Population.

Table 18. Summary of Incidence of Adverse Events by Treatment Group – Safety Population

Parameter	Short Tirofiban (N=)			Eptifibatide (N=)			Long Tirofiban (N=)		
	N of Events	N of Subjects	% of Subjects	N of Events	N of Subjects	% of Patients	N of Events	N of Subjects	% of Subjects
Is it a Serious Adverse Event?									
Yes									
No									
If yes, serious indicator									
Death									
Life-threatening									
Required/prolonged hospitalization									
Significant/permanent disability									
Medically significant									
Is this event ongoing?									
Yes									
No									
Severity of adverse event									
Mild									
Moderate									
Severe									

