Relationship to study drug									
Probably related									
Possibly related									
Unlikely related									

Parameter	Short Tirofiban (N=)			Eptifibatide (N=)			Long Tirofiban (N=)		
	N of Events	N of Subjects	% of Subjects	N of Events	N of Subjects	% of Patients	N of Events	N of Subjects	% of Subjects
Action taken to the study drug									
None									
Discontinued									
Outcome									
Recovered									
Recovered with sequelae									
Unresolved									
Death									
Unknown									

The percentage is based on the number of serious adverse events.

Note: A patient may have reported more than one adverse event. Percentages based on the total number of safety population patients in each treatment group.

Note: This table will also be repeated for Serious Adverse Events.

Table 19. Incidence of Adverse Events by System Organ Class (SOC) and Preferred Term (PT) by Treatment Group – Safety Population

System Organ Class (SOC) Preferred Term (PT)	Short Tirofiban (N=)		Eptifibatide (N=)		Long Tirofiban (N=)	
	Event	Subject (%)	Event	Subject (%)	Event	Subject (%)
TOTAL (ALL SOC/PT)						
SOC 1						
PT 1.1						
PT 1.2						
SOC 2						
PT 2.1						
PT 2.2						

Note: Adverse Events will be coded by MedDRA version x. A patient may have reported more than one adverse event. Percentages based on the total number of safety population patients in each treatment group.

Note: This table will also be repeated for Serious Adverse Events.

Table 20. Descriptive Statistics of Safety Outcomes by Treatment Group – Safety Population

Parameter	Treatment Group		
	Short Tirofiban (N=)	Short Tirofiban (N=)	Short Tirofiban (N=)
REPLACE-2 major bleeding, n (%)			
Yes			
No			
TIMI major bleeding, n (%)			
Yes			
No			
REPLACE-2 minor bleeding, n (%)			
Yes			
No			
TIMI minor bleeding, n (%)			
Yes			
No			
REPLACE-2 plus major bleeding, n (%)			
Yes			
No			
TIMI plus major bleeding, n (%)			
Yes			
No			
Sum of REPLACE-2 major and minor bleeding, n (%)			
Yes			
No			

Parameter	Treatment Group		
	Short Tirofiban (N=)	Short Tirofiban (N=)	Short Tirofiban (N=)
Sum of REPLACE-2 plus major and minor bleeding, n (%)			
Yes			
No			
Sum of TIMI major and minor bleeding, n (%)			
Yes			
No			
Sum of TIMI plus major and minor bleeding, n (%)			
Yes			
No			
Non-bleeding adverse event, n (%)			
Yes			
No			
Thrombocytopenia (< 100,000 cells/ μ L), n (%)			
Yes			
No			
Severe thrombocytopenia (< 50,000 cells/ μ L), n (%)			
Yes			
No			

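### SAP Table 18 has two conflicting denominator footnotes, and one would divide a count of subjects by a count of serious adverse events

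*SAP*

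**What the plan says.** Table 18 in SAP Section 6 is an empty shell for the incidence of adverse events in the safety population. Each arm has three columns: events, subjects, and a percentage headed % of Subjects for the two tirofiban arms and % of Patients for eptifibatide. Its first row block asks whether the event is serious. The next, headed "If yes, serious indicator", splits serious events into death, life-threatening, hospitalization, disability and medically significant. The later blocks cover severity, relationship, action taken and outcome.

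Two denominator statements stand beneath it:

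- "The percentage is based on the number of serious adverse events".
- A Note saying "A patient may have reported more than one adverse event", followed by "Percentages based on the total number of safety population patients in each treatment group".

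A last Note says the table is repeated for SAEs.

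The text rule is in SAP 3.10.3, Analysis of Safety Endpoints. It asks for "the total number and proportion of patients experiencing at least one AE during the treatment period" and says SAEs are to be summarized in the same way. Table 19, on the same population and also repeated for SAEs, carries only the patient denominator.

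**The concern.** The two statements give different denominators for one percentage column, and nothing in the available text says which rows the first governs. A programmer has to choose. If the SAE count is used, the numerator is people and the denominator is events. That ratio is not a proportion of patients, although the heading says it is. It also falls as an arm accumulates more SAEs for the same number of patients affected, so it can make the arm with more events look better.

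What is at stake is how the breakdown of serious events by arm reads in an open-label comparison. Table 18 is the only shell that gives the serious-indicator breakdown, and SAEs are not among the outcomes listed for testing in Table 21. No test result would therefore stand beside these percentages to correct a wrong impression.

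**Working it through.** The plan gives no figure to reproduce, because Table 18 is empty. The check compares the stated rules and then shows what each does to the same counts.

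**1. The rules side by side**

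| Source | Numerator | Denominator |
|---|---|---|
| Table 18, first line | subjects (from the column heading) | SAEs |
| Table 18, Note | subjects | safety population of the arm |
| Table 19, Note | subjects | safety population of the arm |
| SAP 3.10.3 | patients with at least one event | patients |

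The first line is the outlier.

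**2. Formulas**

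For one row in one arm, let *s* be subjects with such an event, *E* the arm's SAEs and *N* its safety population.

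- Incidence: *s/N*.
- First-line percentage: *s/E*.
- Ratio of the second to the first: *N/E*.
- With equal *N* and *s*_A > *s*_B, the order of the arms reverses when *E*_A/*E*_B > *s*_A/*s*_B.

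**3. Assumed counts**

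The documents give no SAE counts. *N* = 250 per arm is assumed, being half of the approximately 500 patients planned for short tirofiban against eptifibatide. It does not describe the long tirofiban arm, which is smaller.

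| Example | Arm | *s* | *E* | *s/E* | *s/N* |
|---|---|---|---|---|---|
| 1 | A | 6 | 30 | 20.0% | 2.4% |
| 1 | B | 4 | 8 | 50.0% | 1.6% |
| 2 | A | 2 | 5 | 40% | 0.8% |
| 2 | B | 3 | 12 | 25% | 1.2% |

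Both examples reverse the order. In the second, the ratio *N/E* is 250/5 = 50 in arm A and 250/12 = 20.8 in arm B.

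**4. How far the reversal depends on the counts**

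Take example 1 and vary only arm A's SAEs. The threshold is 8 × 6/4 = 12.

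| *E*_A | *s/E* in A | Against 50.0% in B |
|---|---|---|
| 8 | 75.0% | order kept |
| 10 | 60.0% | order kept |
| 12 | 50.0% | tie |
| 13 | 46.2% | reversed |
| 20 | 30.0% | reversed |
| 30 | 20.0% | reversed |

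Reversal is possible but not general.

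**5. Which rows the first line can cover**

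In the all-event table it cannot sensibly cover every row. With an assumed 60 subjects having a mild event and 8 SAEs, the result would be 60/8 = 750%. In the serious-indicator rows each subject counted has at least one SAE, so *s* ≤ *E* and the result lies between 0 and 100%. The same is true of every row in the SAE repeat. In those two places no impossible value would expose the wrong denominator.

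**The case against.** The strongest reply is that the plan already settles the matter. SAP 3.10.3, the second Note and Table 19 all point to patients, and the SAE repeat of Table 19 will give patient incidence of SAEs overall and by term with the right denominator. The first line may have lost a marker tying it to the serious-indicator rows when the text was taken from PDF. Table 1 of the SAP uses markers in this way and has a nested denominator for reasons for non-completion. In Table 18 the event and subject counts are printed in each row and *N* heads each arm, so a reader can recompute the incidence. The primary safety endpoint, major bleeding, is reported and tested in Tables 20 and 21, which do not use these percentages.

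Most of this stands, and it limits the size of the point. It does not remove it. A restored marker would only confine the SAE denominator to certain rows, where subjects over events would still be printed as a percentage of subjects. The nested denominator in Table 1 counts patients, so it remains a proportion; this one counts events.

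A reader might infer more: that Table 18 as a whole reports wrong incidences, that it is the main SAE summary, or that the arms will be ranked the wrong way round. The documents support none of these. The shell contains no numbers, and the second Note gives the correct rule. Table 19 supplies SAE incidence separately. Both the reversal and the factors of 20.8 and 50 come from assumed counts.

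**Conclusion.** The point holds as a contradiction in a table shell. Table 18 states two incompatible denominators. The one based on SAEs fits neither the column heading nor SAP 3.10.3, and it would yield a figure that is not a patient incidence. The rows most likely affected are the serious indicators, and possibly the whole SAE repeat. Whether the order of the arms would change depends on counts that the documents do not give.

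The importance is low. Only descriptive percentages are touched, the counts needed to recompute them sit beside them, and neither the Table 21 tests nor the primary analysis is affected. The conclusion rests on the footnotes as they appear in the available text. The likely scope of the first line is a judgement, but the conflict between the two statements is not.

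**What to change.** Delete the line "The percentage is based on the number of serious adverse events" from Table 18 and from its SAE repeat. Compute every percentage of subjects as subjects with at least one such event divided by that arm's safety population. If a breakdown of the SAEs themselves is wanted, add a separately headed percentage of events next to the event count. Use one heading wording in all three arms.

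The cost is one footnote, one denominator in the table program and one column label. No analysis changes and nothing is lost.
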